6.3.1.3 Treatment Group Estimates – Endpoint Analyses

The analysis of covariance (ANCOVA) analyses described in this section exclude de novo subjects. The convulsive seizure frequency per 28 days during the entire OLE Treatment period and the convulsive seizure frequency per 28 days during Month 2 to EOS, CSF_{E1} and CSF_{E2} , respectively, will each be analyzed using an ANCOVA model with age group (<6 years, ≥6 years) and treatment group (4 levels) as factors, and CSF_{BC} and CSF_{CTM} as continuous covariates. The goal of this analysis is to estimate the seizure frequency during (1) the entire OLE treatment, and (2) during Month 2 to EOS, for each of the treatment groups included in the OLE, after adjusting for the other factors in the model. To avoid taking the logarithm of 0, a value of 1 will be added

to a covariate and/or response prior to taking logs. From the general linear model, least squares estimates of treatment means and the corresponding 95% confidence intervals, will be exponentiated and a value of 1 subtracted from the result, (to offset the addition of 1 prior to taking logs), in order to provide estimates and associated 95% confidence intervals on the original scale for the response variable.

Since the ANCOVA relies on assumptions of normality, the analysis will be repeated using a nonparametric method that does not require as stringent assumptions. A nonparametric ANCOVA will be used to analyze the data, with ranks of the CSF_{BC}, and ranks of the CSF_{CTM} as covariates and ranks of the response (CSF_{E1} or CSF_{E2}); other terms/factors in the model will be the same as for the parametric ANCOVA.

Due to certain portions of the core studies remaining blinded, the ANCOVA analyses described in this section will not be submitted with the Japanese interim analysis.

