6.3.1.4 Treatment Group Estimates – CSF Over Time

The general linear mixed effects model with repeated measures (i.e. MMRM) described in this section exclude de novo subjects. Analyses will be performed for the convulsive seizure frequency per 28 days, over time. In these analyses, the CSF_{CSFW} will not be included in the model. A MMRM will be employed to estimate the mean convulsive seizure frequency per 28 days, over time, for each treatment group. The model will include CSF_{BC} and CSF_{CTM} as fixed covariates; time (14 levels for Month1, Month2, Month3, Month 4-6, Month 7-9, Month 10-12, Month 12-15, Month 16-18, Month 19-21, Month 22-24, Month 25-27, Month 28-30, Month 31-33, and Month 34-36) as a fixed effect; age stratum (2 levels) as a fixed effect; treatment group (4 levels) as a fixed effect; and subject as a random effect.

CSF will be log transformed prior to analysis, and a value of 1 may be added to avoid taking the logarithm of 0.

The purpose of this modeling is to obtain least-squares adjusted means over time for the frequency of convulsive seizures per 28 days along with 95% confidence intervals.

While we seek to estimate the means over time, the variances and covariances are nuisance parameters and need to be estimated to provide associated standard errors for the treatment estimates. For the MMRM, an unstructured covariance matrix will be used. [If the model experiences convergence issues, a different covariance structure may be explored from the available choices in SAS PROC MIXED, and the covariance structure with the smallest AIC will be chosen.]

The model adjusted means and associated confidence limits will be plotted against time.

Furthermore, exploratory analysis will be carried out using a general linear model that includes the mean daily dose during OLE period (categorized as low, medium, and high) as explanatory variable, and the same factors used in the MMRM described above.

Due to certain portions of the core studies remaining blinded, the MMRM analyses described in this section will not be submitted with the Japanese interim analysis.

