[1] Baseline and overall OLE values were log transformed prior to analysis. To avoid taking log of 0, a value of 1 was added to each subject's convulsive seizure frequency value (with the exception of the Baseline (Core) value) before log transformation.

[2] Results are based on an ANCOVA model with treatment group (four levels excluding group that contained all subjects enrolled in 1503 – regardless of feeder study) and age group (< 6 years, ≥6 years) as factors, log baseline convulsive seizure frequency as a covariate, CSF during Core Study as another covariate, and log convulsive seizure frequency (overall OLE period, or Month2 to EOS) as response.

[3] Values obtained from the ANCOVA model were exponentiated to get the corresponding values on the original scale.

Programming note: Use PROC MEANS for summary stats, and PROC GLM for parametric model analysis.

Table 14.2.1.3
Convulsive seizure frequency per 28 days - ENDPOINT: Nonparametric Analysis
mITT Population

Statistics	PBO-ZX008 OL (N = XX)	ZX 0.2 – ZX008 OL (N = XX)	ZX 0.5 – ZX008 OL (N = XX)	ZX 0.8 – ZX008 OL (N = XX)	ZX008 OL (N = XX)
ENDPOINT1: OLE TREATMENT PERIOD ANALYSIS					
Baseline (Core) Ranks[1]: Summary Statistics					
N	XX	XX	XX	XX	XX
Mean	XX.X	XX.X	XX.X	XX.X	XX.X
SD	XX.XX	XX.XX	XX.XX	XX.XX	XX.XX
Median	XX.X	XX.X	XX.X	XX.X	XX.X
Min	XX	XX	XX	XX	XX
Max	XX	XX	XX	XX	XX
Core Study Ranks[1]: Summary Statistics					
N	XX	XX	XX	XX	XX
Mean	XX.X	XX.X	XX.X	XX.X	XX.X
SD	XX.XX	XX.XX	XX.XX	XX.XX	XX.XX
Median	XX.X	XX.X	XX.X	XX.X	XX.X
Min	XX	XX	XX	XX	XX
Max	XX	XX	XX	XX	XX
OLE Period Ranks[1]: Summary Statistics					
N	XX	XX	XX	XX	XX
Mean	XX.X	XX.X	XX.X	XX.X	XX.X
SD	XX.XX	XX.XX	XX.XX	XX.XX	XX.XX
Median	XX.X	XX.X	XX.X	XX.X	XX.X
Min	XX	XX	XX	XX	XX
Max	XX	XX	XX	XX	XX
OLE Period: Nonparametric Model Summary[1]					
Results on rank scale					
Least Squares Mean (SE) [2]	XX.X (XX.XX)	XX.X (XX.XX)	XX.X (XX.XX)	XX.X (XX.XX)	XX.X (XX.XX)
95% CI for Least Squares Mean [2]	(XX.X,XX.X)	(XX.X,XX.X)	(XX.X,XX.X)	(XX.X,XX.X)	(XX.X,XX.X)

TLF Shells

Zogenix International Limited
ZX008-1503

Statistics	PBO-ZX008 OL (N = XX)	ZX 0.2 – ZX008 OL (N = XX)	ZX 0.5 – ZX008 OL (N = XX)	ZX 0.8 – ZX008 OL (N = XX)	ZX008 OL (N = XX)
MONTH2 to EOS ANALYSIS					
Baseline (Core) Ranks[1]: Summary Statistics					
N	XX	XX	XX	XX	XX
Mean	XX.X	XX.X	XX.X	XX.X	XX.X
SD	XX.XX	XX.XX	XX.XX	XX.XX	XX.XX
Median	XX.X	XX.X	XX.X	XX.X	XX.X
Min	XX	XX	XX	XX	XX
Max	XX	XX	XX	XX	XX
Core Study Ranks[1]: Summary Statistics					
N	XX	XX	XX	XX	XX

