Least Squares Mean[2]	XX.X	XX.X	XX.X	XX.X	XX.X
95% CI[2]	(XX.X,XX.X)	(XX.X,XX.X)	(XX.X,XX.X)	(XX.X,XX.X)	(XX.X,XX.X)

.... (Repeat for months 2, 3, 6, 9, 12, 15, 18, 21, 24, 27, 30, 33,
and 36

mITT = Modified intent-to-treat population; CI = Confidence Interval; SD = Standard Deviation; SE = Standard Error.

Note: this table excludes de Novo subjects.

[1] Baseline and overall OLE values were log transformed prior to analysis. To avoid taking log of 0, a value of 1 was added to each subject's convulsive seizure frequency value (the response variable) for each timepoint in the OLE period before taking the natural logarithm.

[2] Results are based on a general linear model with fixed effects for treatment group (four levels excluding group that contained all subjects enrolled in 1503 – regardless of feeder study) and age group (< 6 years, ≥6 years), time (Months 1, 2, 3, 6, 9, 12, 15, 18, 21, and 24) and log baseline convulsive seizure frequency as a covariate; and random effects for subject (repeated over time). The dependent variable is log convulsive seizure frequency (overall OLE period) as response.

[3] Values obtained from the ANCOVA model were exponentiated to get the corresponding values on the original scale.

Programming note: Use PROC MEANS for summary stats

For MMRM model, use PROC MIXED. Before calling the PROC, please add 1 to the Month1, Month2, ... Month24 CSF values, then take the natural log (log to base e) of these values to be used in the model. PROC MMRM for parametric model analysis. The LSMeans are the LSMeans for the time*treatment interaction terms. See stats manual.

Programming Notes: Use the shell for 14.2.1.4 for

Table 14.2.1.5
Convulsive seizure frequency per 28 days, Over Time – Parametric Analysis Using Mean Daily Dose
mITT Population

In place of treatment groups, categorize subjects into three treatments depending on their mean daily dose during the OLE Treatment period as Low, Medium, and High. See SAP.

Categories for Low, Medium, High depending on the following doses of ZX008

<0.4 mg/kg = Low

0.4-0.6 mg/kg = Medium

>0.6 mg/kg = High

[figure not shown]
Table 14.2.1.6
% of Subjects with Changes in AED medications during 1st 6 months of OLE Treatment Period
mITT Population

OLE Period	PBO-ZX008 OL (N = XX)	ZX 0.2 – ZX008 OL (N = XX)	ZX 0.5 – ZX008 OL (N = XX)	ZX 0.8 – ZX008 OL (N = XX)	ZX008 OL (N = XX)
Any Change in AED medication during the 1 st 6 months	XX (XX%)	XX (XX%)	XX (XX%)	XX (XX%)	XX (XX%)

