Month 1	XX (XX%)	XX (XX%)	XX (XX%)	XX (XX%)	XX (XX%)
Month 2	XX (XX%)	XX (XX%)	XX (XX%)	XX (XX%)	XX (XX%)
Month 3	XX (XX%)	XX (XX%)	XX (XX%)	XX (XX%)	XX (XX%)
Month 4	XX (XX%)	XX (XX%)	XX (XX%)	XX (XX%)	XX (XX%)
Month 5	XX (XX%)	XX (XX%)	XX (XX%)	XX (XX%)	XX (XX%)
Month 6	XX (XX%)	XX (XX%)	XX (XX%)	XX (XX%)	XX (XX%)

mITT = Modified intent-to-treat population ; Months are defined in 30 day increments. Month1=Day1-Day30, Month2=Day31-Day60, and so on.

Programming Note: we need to determine what a change in AED medication is

Figure 14.2.1.7
Graph of means for convulsive seizure frequency per 28 days during OLE Treatment Period
mITT Population

mITT = Modified intent-to-treat population

Programming Note: This plots the means from Table 14.2.1.1.1

Figure 14.2.1.8

Graph of model adjusted means for Convulsive seizure frequency per 28 days – mITT Population

Programming note: Forest plots for the model adjusted means and CIs

Programming note: Repeat Figure 14.2.1.7 using the following 3 treatment groups: Low, Medium, and High to produce

Figure 14.2.1.9

Graph of convulsive frequency per 28 days, Over Time, Using Mean Daily Dose
mITT Population

Table 14.2.2.1
Percent Reduction in Convulsive Seizure Frequency, OLE Treatment Period
mITT Population

Time Period	Distribution of Percentage Change from Baseline(Core) in convulsive Seizure Frequency[1]	PBO-ZX008 OL (N = XX)	ZX 0.2 – ZX008 OL (N = XX)	ZX 0.5 – ZX008 OL (N = XX)	ZX 0.8 – ZX008 OL (N = XX)	ZX008 OL # (N = XXX)	De Novo Subjects (N = XXX)
OLE Period	≥25%: n (%)	XX (XX.X%)	XX (XX.X%)	XX (XX.X%)	XX (XX.X%)	XX (XX.X%)	XX (XX.X%)
	95%CI*	XX.X%, XX.X%	XX.X%, XX.X%	XX.X%, XX.X%	XX.X%, XX.X%	XX.X%, XX.X%	XX.X%, XX.X%
	≥50%: n (%)	XX (XX.X%)	XX (XX.X%)	XX (XX.X%)	XX (XX.X%)	XX (XX.X%)	XX (XX.X%)
	95%CI*	XX.X%, XX.X%	XX.X%, XX.X%	XX.X%, XX.X%	XX.X%, XX.X%	XX.X%, XX.X%	XX.X%, XX.X%
Month 1	≥25%: n (%)	XX (XX.X%)	XX (XX.X%)	XX (XX.X%)	XX (XX.X%)	XX (XX.X%)	XX (XX.X%)
	95%CI*	XX.X%, XX.X%	XX.X%, XX.X%	XX.X%, XX.X%	XX.X%, XX.X%	XX.X%, XX.X%	XX.X%, XX.X%
	≥50%: n (%)	XX (XX.X%)	XX (XX.X%)	XX (XX.X%)	XX (XX.X%)	XX (XX.X%)	XX (XX.X%)
	95%CI*	XX.X%, XX.X%	XX.X%, XX.X%	XX.X%, XX.X%	XX.X%, XX.X%	XX.X%, XX.X%	XX.X%, XX.X%
Month 1	≥75%: n (%)	XX (XX.X%)	XX (XX.X%)	XX (XX.X%)	XX (XX.X%)	XX (XX.X%)	XX (XX.X%)
	95%CI*	XX.X%, XX.X%	XX.X%, XX.X%	XX.X%, XX.X%	XX.X%, XX.X%	XX.X%, XX.X%	XX.X%, XX.X%
	=100%: n (%)	XX (XX.X%)	XX (XX.X%)	XX (XX.X%)	XX (XX.X%)	XX (XX.X%)	XX (XX.X%)

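### The table shells exponentiate log(CSF+1) without subtracting the added 1: this contradicts Section 6.3.1.3 for the ANCOVA and leaves the MMRM with no correct back-transformation rule

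*SAP*

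**What the plan says.** **ANCOVA, SAP body.** Section 6.3.1.3 covers CSF over the whole OLE period and from Month 2 to EOS. On the offset it says: "To avoid taking the logarithm of 0, a value of 1 will be added". The least squares estimates and their 95% limits "will be exponentiated and a value of 1 subtracted from the result, (to offset the addition of 1 prior to taking logs".

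**ANCOVA, shell.** Footnote [1] of Table 14.2.1.2 also adds the offset: "a value of 1 was added to each subject's convulsive seizure frequency value (with the exception of the Baseline (Core) value) before log transformation". The original-scale mean and interval rows, for both endpoints, carry footnote [3]: "Values obtained from the ANCOVA model were exponentiated to get the corresponding values on the original scale". It does not mention a subtraction.

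**MMRM, SAP body.** Section 6.3.1.4 says: "CSF will be log transformed prior to analysis, and a value of 1 may be added to avoid taking the logarithm of 0". It gives no rule for returning to the original scale.

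**MMRM, shell.** In Table 14.2.1.4, footnote [1] adds 1 to the response "for each timepoint in the OLE period before taking the natural logarithm", and the programming note repeats that instruction. Footnote [3] is the same exponentiate-only sentence as in Table 14.2.1.2 and still refers to an ANCOVA. The original-scale rows cite footnote [2], which describes the model, so no row points to [3]. Table 14.2.1.5 reuses this shell with dose groups in place of feeder-study groups.

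**Related outputs.** The note for Figure 14.2.1.8 is "Forest plots for the model adjusted means and CIs" and states no scale. The seizure-free-day MMRM shells, Tables 14.2.5.2 and 14.2.5.3, use the same pattern of adding 1 and then exponentiating.

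**The concern.** The added 1 exists only so that zeros can be logged. If it is not removed on the way back, the rows labelled as original scale estimate CSF+1 rather than CSF. These rows hold the model-adjusted values of the two key effectiveness measures and of CSF over time.

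The values would be too high, could not fall below 1 for any non-negative underlying frequency, and would stand beside raw summary statistics in the same tables that carry no offset. A reader comparing the two would see a gap that comes from the programming and not from the model. Adding 1 to both sides of a comparison also pulls group ratios toward 1 for anyone who forms them from the printed means.

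**Working it through.** The SAP states no figure on this point, so there is nothing of its own to reproduce. The inputs are the transformation rules in Sections 6.3.1.3 and 6.3.1.4 and in the footnotes of Tables 14.2.1.2 and 14.2.1.4.

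**Step 1: algebra.** Let m be a least squares mean, or a confidence limit, on the scale log(CSF+1).

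- Section 6.3.1.3 rule: exp(m) − 1.
- Shell footnote [3] rule: exp(m).
- Difference: exp(m) − [exp(m) − 1] = 1 for every m.

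The shift is the same for the mean and for both limits, so the interval keeps its width and moves up by 1.0.

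**Step 2: relative size.** If the correctly back-transformed value is x, the shell prints x + 1 and the relative overstatement is 1/x. The values of x below are assumed.

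| Correct value, per 28 days | Printed by the shell rule | Overstatement |
|---|---|---|
| 0 | 1 | not defined |
| 2 | 3 | 50% |
| 5 | 6 | 20% |
| 10 | 11 | 10% |
| 20 | 21 | 5% |
| 40 | 41 | 2.5% |

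**Step 3: check in a fitted model.** A four-group ANCOVA on log(CSF+1) was simulated with group sizes 120, 80, 80 and 40 from SAP Table 1. The seizure distribution was assumed, so this only illustrates the mechanism. For the first group the shell rule gives 6.652 (5.740 to 7.709) and the Section 6.3.1.3 rule gives 5.652 (4.740 to 6.709). The other three groups show the same difference of 1.000 in the mean and both limits.

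**Step 4: where each rule applies.**

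| Output | Is 1 added? | Is subtraction stated anywhere? |
|---|---|---|
| Table 14.2.1.2 (ANCOVA) | Yes | Yes in Section 6.3.1.3, not in the shell |
| Tables 14.2.1.4 and 14.2.1.5 (MMRM) | Yes, per shell | No |
| Tables 14.2.5.2 and 14.2.5.3 (seizure-free days) | Yes, per shell | No |
| Table 14.2.1.3 (rank ANCOVA) | No log step | Not needed |
| Table 14.2.6.1 (change from baseline) | No log stated | Not needed |

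**The case against.** The strongest defence concerns the ANCOVA. The SAP body gives the right rule and explains it, and footnote [3] of Table 14.2.1.2 is an output note, not code. The programming note there names only the SAS procedures. A careful programmer working from Section 6.3.1.3 would get the right answer. This stands: for Table 14.2.1.2 the defect is a conflict between text and shell, not a settled wrong number.

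For the MMRM, footnote [3] looks like leftover text, since it names the wrong model and no row cites it. The programming note also sends the reader to a statistics manual that is not part of the SAP, so the code that will be run cannot be known from this document. That is fair, but it does not rescue the plan: the only back-transformation the SAP states for these tables is the wrong one.

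A reader might infer that every model-based seizure frequency in the report is wrong, or that the evidence of benefit is affected. The documents do not support either. Log-scale rows carry no back-transformation, the rank ANCOVA has no log step, and Table 14.2.6.1 models change from baseline with no log stated. The key hypothesis in Section 6.3.1.2 is tested with a Wilcoxon signed rank test, which this does not touch, as are the descriptive and responder tables.

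The effect on ratios (for example 2/10 = 0.20 read as 3/11 = 0.27) concerns a quantity the shells do not print, and Section 6.1.2 plans no formal comparison between groups. Figure 14.2.1.8 is affected only if it is drawn on the original scale. Appendix 1 marks Tables 14.2.1.2, 14.2.1.4 and 14.2.1.5 for none of the interim, 120-day or Japan reports, so the exposure is the final report.

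**Conclusion.** The point holds for the original-scale rows of Tables 14.2.1.2, 14.2.1.4 and 14.2.1.5. The first contradicts Section 6.3.1.3. For the other two the SAP contains no instruction to subtract the 1, so the stated rule gives a wrong result.

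If the footnotes are programmed as written, the least squares means and both confidence limits are exactly 1.0 per 28 days too high. That figure is algebraic and rests on no assumption about the data. The percentages do depend on the level of CSF, which the SAP does not give: 50% at 2, 10% at 10, 2.5% at 40. The shift overstates seizure frequency, so for these tables it works against the drug, but the reported estimates would still be wrong.

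**What to change.** - **Tables 14.2.1.2 and 14.2.1.4, footnote [3]:** state that the least squares mean and both confidence limits are exponentiated and 1 is then subtracted. Carry this to Table 14.2.1.5.
- **Table 14.2.1.4:** point the original-scale rows to footnote [3] and correct the model name in that footnote.
- **Section 6.3.1.4:** change *may* be added to *will* be added, and state the same back-transformation.
- **Tables 14.2.5.2 and 14.2.5.3:** apply the same wording wherever 1 is added.
- **Figure 14.2.1.8:** state the scale, and apply the rule if the plot is on the original scale.

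The cost is a few words in the SAP and shells and one line of code. No data, model or test changes.

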6.3.2.7 Incidence of Status Epilepticus Episodes

The incidence of status epilepticus during the OLE treatment period will be evaluated based on cases captured as such with treatment at hospitals or other treatment centers, those entered as adverse events (including SAEs) into the safety database, and also as convulsive seizures lasting longer than 10 min from the seizure diary. A single seizure meeting more than one of these criteria will be counted once. According to the ILAE, seizures of this duration are to be considered SE.

The number and percentage of subjects with status epilepticus recorded as an AE will be presented by treatment group and overall.

In addition, from the diary data, the number and percentage of subjects having convulsive seizures with duration >10 min during OLE will be reported by treatment group and overall.

Additionally, the number and percentage of subjects having an SE episode or a seizure with duration > 10 minutes will be summarized by treatment group and overall.

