Min, Max	Xx, xx	Xx, xx	Xx, xx	Xx, xx	Xx, xx	Xx, xx
Occurrences per 100 subject years [1]	xxx.xx	xxx.xx	xxx.xx	xxx.xx	xxx.xx	xxx.xx
EEG						
No. of subjects (%)	XX (%)	XX (%)	XX (%)	XX (%)	XX (%)	XX (%)
Number of occurrences for subjects with at least one						
Mean (SD)	XX.X (xx.xx)	XX.X (xx.xx)	XX.X (xx.xx)	XX.X (xx.xx)	XX.X (xx.xx)	XX.X (xx.xx)
Median	XX.X	XX.X	XX.X	XX.X	XX.X	XX.X
Min, Max	XX, xx	XX, XX	XX, xx	XX, XX	XX, XX	XX, XX
Occurrences per 100 subject years [1]	xxx.xx	xxx.xx	xxx.xx	xxx.xx	xxx.xx	xxx.xx
Repeat for the following						
EKG						
ECHO						
PET Scans						
MRI						
X Ray						
CT Scan						

TLF Shells

Zogenix International Limited

ZX008-1503

Surgery						
Lumber Puncture / Spinal Tap						
Other						

mITT = Intent-to-treat;

The mean, median, min and max describe the number of events or procedures per subject for those subjects who had at least one event or procedure.

[1] Occurrence rate is based on the total number of occurrences during the study divided by the total number of subject years of followup for subjects in the column. Multiple occurrences for the same subject are included.

TLF Shells

Zogenix International Limited
ZX008-1503

Programming note: Use the same Table 14.2.8.1 shell to produce

Table 14.2.8.2
Hospitalization and Other Healthcare Resource Utilization to Treat Seizure
mITT Population (Japan)

Table 14.2.9.1
 Number of episodes of status epilepticus (SE)
 mITT Population

	PBO-ZX008 OL (N = XX)	ZX 0.2 - ZX008 OL (N = XX)	ZX 0.5 - ZX008 OL (N = XX)	ZX 0.8 - ZX008 OL (N = XX)	ZX008 OL (N = XX)	De Novo Subjects (N = XX)
Subjects with at Least One episode of status epilepticus reported as AE[1]	XX (XX.X%)	XX (XX.X%)	XX (XX.X%)	XX (XX.X%)	XX (XX.X%)	XX (XX.X%)
Number of seizures reported greater than 10 min[2]						
No. of subjects	XX	XX	XX	XX	XX	XX
Mean per subject	XX.X	XX.X	XX.X	XX.X	XX.X	XX.X
Std. Error	XX.XX	XX.XX	XX.XX	XX.XX	XX.XX	XX.XX
Median	XX.X	XX.X	XX.X	XX.X	XX.X	XX.X
Min	XX	XX	XX	XX	XX	XX
Max	XX	XX	XX	XX	XX	XX
Total unique events: SE as an AE, plus seizures >10 min						
No. (%) of Subjects with at least one event	XX (XX.X%)	XX (XX.X%)	XX (XX.X%)	XX (XX.X%)	XX (XX.X%)	XX (XX.X%)
Age group <6 years	XX (XX.X%)	XX (XX.X%)	XX (XX.X%)	XX (XX.X%)	XX (XX.X%)	XX (XX.X%)
95% Exact CI	(xx.x%,xx.x%)	(xx.x%,xx.x%)	(xx.x%,xx.x%)	(xx.x%,xx.x%)	(xx.x%,xx.x%)	(xx.x%,xx.x%)
Age group ≥6 years	XX (XX.X%)	XX (XX.X%)	XX (XX.X%)	XX (XX.X%)	XX (XX.X%)	XX (XX.X%)

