95% Exact CI	(xx.x%,xx.x%)	(xx.x%,xx.x%)	(xx.x%,xx.x%)	(xx.x%,xx.x%)	(xx.x%,xx.x%)	(xx.x%,xx.x%)
Total unique events: SE as an AE, plus seizures >10 min						
Unique events						
1	XX (XX.X%)	XX (XX.X%)	XX (XX.X%)	XX (XX.X%)	XX (XX.X%)	XX (XX.X%)
2	XX (XX.X%)	XX (XX.X%)	XX (XX.X%)	XX (XX.X%)	XX (XX.X%)	XX (XX.X%)
3	XX (XX.X%)	XX (XX.X%)	XX (XX.X%)	XX (XX.X%)	XX (XX.X%)	XX (XX.X%)
.....						

mITT = Intent-to-treat;

[1] Any AE with Status Epilepticus or presumed Epilepticus

[2] This includes all single seizures >10 minutes in duration as recorded in the subject's seizure diary. For each subject, the number of episodes is calculated; then the number per subject for each treatment group is obtained by summing across subjects in each group and dividing by number of subjects in that treatment group who had single seizures > 10 min.

Programming note: Use the same Table 14.2.9.1 shell for

Table 14.2.9.1.1
Number of episodes of status epilepticus (SE)
mITT Population (Japan)

Table 14.2.9.2
Duration of Seizures
mITT Population

Percentage of seizures by duration	PBO-ZX008 OL (N = XX)	ZX 0.2 – ZX008 OL (N = XX)	ZX 0.5 – ZX008 OL (N = XX)	ZX 0.8 – ZX008 OL (N = XX)	ZX008 OL (N = XX)	De Novo Subjects (N = XX)
Baseline						
<2 min	XX.XX	XX.XX	XX.XX	XX.XX	XX.XX	NA
2-10 min	XX.XX	XX.XX	XX.XX	XX.XX	XX.XX	NA
>10 min	XX.XX	XX.XX	XX.XX	XX.XX	XX.XX	NA
OLE Treatment Period						
<2 min	XX.XX	XX.XX	XX.XX	XX.XX	XX.XX	XX.XX
2-10 min	XX.XX	XX.XX	XX.XX	XX.XX	XX.XX	XX.XX
>10 min	XX.XX	XX.XX	XX.XX	XX.XX	XX.XX	XX.XX

mITT = modified Intent-to-treat; 95% CI are based on the exact (Clopper-Pearson) method. NA = Not Applicable.

Programming notes:

To calculate the probability of a seizure <2 min. for a given treatment group, for each subject, calculate the proportion of seizures < 2 min. For example, if the subject has a total of 5 seizures with 2 being <2 min in duration, their proportion is 2/5. Add these proportions for all subjects in the treatment group, and divide the total by the number of subjects to get the treatment group proportion of subjects with seizure duration <2 min. Then multiply the result by 100 to get the percentage.

Repeat for the other treatment groups. Repeat for seizure durations 2-10 min., and for >10 min.

Table 14.2.10.1
 Clinical Global Impression of Improvement, Parent/Caregiver Rating
 mITT Population

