	Core Study(T+M)	Yyyy-mm-dd	Single, or Cluster>	Type 2	2-10 min		2
	OLE Treatment	Yyyy-mm-dd	Single, or Cluster>	Type 3	>10min		3*
				...			4
							...
XXXX							
XXXX							
.							
.							
.							

*Imputed – the number of seizures in the cluster was not stated. It was imputed as 3.

**With reference to start of OLE Study.

Programming note: Present the subject identifier (grayed out) on all lines after the first line for a subject.

Non-convulsive Seizures:

B2: FOCAL WITHOUT CLEAR OBSERVABLE MOTOR SIGNS (i.e. autonomic changes like color change or pupillary dilation, and no motor signs)

E: ABSENCE OR ATYPICAL ABSENCE

F: MYOCLONIC

H: ATONIC – not resulting in a drop

K: INFANTILE SPASMS (if under 3 years of age)

L: EPILEPTIC SPASMS (if 3 years of age and older)

TLF Shells

Zogenix International Limited
ZX008-1503

M: NON CONVULSIVE STATUS (greater than 30 min)

O: OTHER

Programming Note: Use the 16.2.6.2 shell for

Listing 16.2.6.2.1

Non-Convulsive seizure – by type, duration and number of occurrences per subject (Diary data) (Japan)

Listing 16.2.6.3

Duration of the Longest interval between convulsive seizures and convulsive seizure free days per subject

Treatment group: XXX

Subject Identifier	Period	Number of Days with a Seizure Occurrence	Longest interval between convulsive seizures	Convulsive seizure free days
XXXX	Baseline(Core)	Xxx	xx	XX
	Core Study(T+M)	Xxx	Xxx	Xxx
	OLE Treatment	xxx	xxx	xxx
XXXX				
XXXX				
.				
.				
.				

Programming Note: Present the subject identifier (grayed out) on all lines after the first line for a subject. Use the 16.2.6.3 shell for

Listing 16.2.6.3.1

Duration of the Longest interval between convulsive seizures and convulsive seizure free days per subject (Japan)

Listing 16.2.6.4
 Percent reduction in convulsive seizure frequency from baseline

Treatment group: XXX

Subject ID	mITT Population?	Period	CSF per 28 Days	% Change from Baseline(Core)	≥25%? (Y/N)	≥50%? (Y/N)	≥75% (Y/N)	=100%? (Y/N)
XXXX	Y	Baseline (Core)	xxx.x					
		Core Study (T+M)	xxx.x	xxx.x	Y	N	Y	N
		Month1-EOT	xxx.x	xxx.x	Y	Y	N	N
		Month2-EOT	xxx.x	xxx.x	Y	N	N	N
XXXX	Y	Baseline (Core)	xxx.x					
		Core Study (T+M)	xxx.x	xxx.x	Y	Y	Y	N
		Month1-EOT	xxx.x	xxx.x	Y	Y	Y	N
		Month2-EOT	xxx.x	xxx.x	Y	Y	Y	N
XXXX	Y	Baseline (Core)	xxx.x					
		Core Study (T+M)	xxx.x	xxx.x	Y	Y	Y	N
		Month1-EOT	xxx.x	xxx.x	Y	Y	Y	N
XXXX	Y	Month2-EOT	xxx.x	xxx.x	Y	Y	Y	Y

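### Shell Table 14.2.9.1 and the last summary in Section 6.3.2.7 count any diary seizure over 10 minutes as status epilepticus, and the shell names no hospital source, so neither matches the definition in 6.3.2.7

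*SAP*

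**What the plan says.** Section 2.2 lists the incidence of status epilepticus among the secondary objectives. Section 6.3.2.7 says how cases are found. They are "evaluated based on cases captured as such with treatment at hospitals or other treatment centers"; they are "those entered as adverse events (including SAEs) into the safety database"; and they are counted "also as convulsive seizures lasting longer than 10 min from the seizure diary". Duplicates are handled explicitly: "A single seizure meeting more than one of these criteria will be counted once".

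The section then plans three outputs, each a number and percentage of subjects by treatment group and overall:

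1. Status epilepticus recorded as an adverse event.
2. From the diary, "the number and percentage of subjects having convulsive seizures with duration >10 min during OLE".
3. Either a status epilepticus episode or a seizure longer than 10 minutes. This one does not say convulsive.

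Shell Table 14.2.9.1 has an adverse-event row, a row for seizures reported as longer than 10 minutes, and combined rows headed "Total unique events: SE as an AE, plus seizures >10 min". Footnote [2] defines the diary row: "This includes all single seizures >10 minutes in duration as recorded in the" subject's diary. It adds that the mean is taken over subjects who had such a seizure. The same shell produces the Japan table, 14.2.9.1.1.

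**The concern.** A programmer works from the shell. If the shell's rule for a case differs from the rule in the text, the reported incidence answers a different question from the one in Section 6.3.2.7. Nothing in the output would show the difference.

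Two elements differ. The diary part is not limited to convulsive seizures, although the diary also times non-convulsive ones. The hospital or treatment-centre source appears in no row, footnote or programming note of the table. The first difference can add subjects and the second can remove them. This is an open-label study with descriptive summaries only, so no test is affected. What is at stake is the accuracy of a reported incidence for a serious seizure outcome.

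**Working it through.** There is no stated figure to reproduce, so the check compares the texts.

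| Element | 6.3.2.7, opening paragraph | 6.3.2.7, planned outputs | Table 14.2.9.1 |
|---|---|---|---|
| Adverse events | Yes | Yes (output 1) | Yes, footnote [1] |
| Diary over 10 min | Convulsive only | Convulsive in output 2; unrestricted in output 3 | Unrestricted in row labels and footnote [2] |
| Hospital or treatment centre | Yes | Not named; at most implied by a status epilepticus episode in output 3 | Not named |
| Each seizure counted once | Yes | Not repeated | Yes, but over two sources |
| Diary statistic | Not stated | n and % of subjects | Number of subjects without %, then mean, standard error, median and range |

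**Can an unrestricted diary rule pick up non-convulsive events?** Yes. Listing 16.2.6.2 shows non-convulsive seizures by type and duration, with a category above 10 minutes. Its types include "M: NON CONVULSIVE STATUS (greater than 30 min"), and any such entry exceeds 10 minutes by definition. The convulsive types are listed separately in Listing 16.2.6.1 (A, B1, C, D, G, I and J), so the filter already exists.

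**Can the missing hospital source lose cases?** Possibly. Section 6.3.2.7 lists it apart from adverse events, and the SAP nowhere says that every hospital-treated case is also entered as an adverse event.

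**Net effect on the number of subjects.** Let X be the subjects with a status epilepticus adverse event or a convulsive diary seizure over 10 minutes. Let H be those with a hospital-treated case and N those with a non-convulsive diary seizure over 10 minutes.

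- Definition in 6.3.2.7: |X ∪ H| = |X| + |H outside X|
- Shell read literally: |X ∪ N| = |X| + |N outside X|
- Shell minus definition = |N outside X| − |H outside X|

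Both terms are zero or more, and the SAP gives a value for neither. The net difference can therefore have either sign. Even a net difference of zero would not mean that the same subjects are counted.

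**Can the reader recover the defined figure elsewhere?** In part. Table 14.2.4.1 gives subjects (n and %) and episodes for convulsive seizures over 10 minutes, which supplies output 2. It cannot supply the combined unique-event rows, because the overlap with adverse events and hospital cases is not shown. It also has no Japan copy in the list of tables, whereas Table 14.2.9.1.1 is marked for the 2020 Japan report.

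**The case against.** The strongest reply is that the shell's combined row follows the third output of 6.3.2.7, which also omits convulsive and does not name hospitals. That is right. A reader might infer that the shell alone departs from a clear text, and the document does not support this: 6.3.2.7 is inconsistent within itself, and correcting only the shell would leave it so.

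A second reply is that dropping the adjective is shorthand. Table 14.2.9.2 is titled simply as duration of seizures, although Section 6.3.2.8 concerns convulsive ones. This is plausible, and it means nobody can say that non-convulsive entries will be counted. But footnote [2] is worded to include all single seizures, and Table 14.2.4.1 does say convulsive where that is meant. The rule needs stating.

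Third, hospital-treated status epilepticus would usually also be an adverse event. Section 6.4.1 defines adverse events broadly, and Listing 16.2.7.1 has hospitalization as a seriousness criterion. Admissions to treat seizures are also tabulated in Table 14.2.8.1. A reader might infer that hospital cases are lost; the SAP shows only that they can be.

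Fourth, a reader might object to the mean per subject because it divides by affected subjects only and so cannot fall below 1. The documents do not make this an error. Section 6.3.2.7 plans no mean, footnote [2] discloses the denominator, and Table 14.2.8.1 uses the same convention. Incidence is carried by the n (%) rows, with exact intervals by age group. All that stands is that the label should say the mean is conditional.

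**Conclusion.** The point holds as a mismatch of case definition. The opening paragraph of 6.3.2.7 sets three de-duplicated sources with a convulsive diary criterion. The last summary of that section and Table 14.2.9.1 both drop the convulsive restriction, and the table's unique-event rows name only two sources. The diary row also lacks the percentage that 6.3.2.7 plans.

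Followed literally, the table can add subjects with long non-convulsive entries and omit hospital-treated cases that are not adverse events. The size is unknown: the SAP gives neither the frequency of non-convulsive seizures over 10 minutes nor the share of hospital-treated cases outside adverse-event reporting, and any percentage put on either would be a guess. The conclusion assumes that the opening paragraph of 6.3.2.7 is the intended definition and that programmers follow the shell as written. It does not extend to the denominator of the mean.

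**What to change.** Make the same change in three places: the last sentence of Section 6.3.2.7, Table 14.2.9.1 with footnote [2], and the Japan copy, Table 14.2.9.1.1.

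- Restrict the diary part to the convulsive types of Listing 16.2.6.1, in row labels and footnote.
- Add cases treated at hospitals or other centres to the unique-event rows, with the count-once rule applied across all three sources.
- Give n (%) of subjects in the diary row.
- Show non-convulsive seizures over 10 minutes, including type M, on a separate line.
- Keep the mean if wished, labelled as among subjects with at least one such seizure.

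The cost is shell wording, a filter on seizure type and a source flag. Diary type and duration are already recorded, and Section 6.3.2.6.1 says hospitalization data are captured in the CRF. The SAP does not say where treatment at other centres is recorded for all subjects, so that should be confirmed and stated.
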